intervention effects. Data set documentation will then be developed and distributed to the study team. Before carrying out analyses addressing each of the research questions, an analysis plan will be formally presented to the study team and Project Advisory Board so a wide range of expertise and experience is brought to bear on each work product of the team.

Some key features of the stepped wedge design require special consideration in the planned analyses. First, the design involves unidirectional cross-over from the control arm to the intervention arm for all PCPs. This has to be captured by an indicator specific to PCP and time point. Second, there are natural hierarchical structures in the data with PCPs nested within clinics, patients nested within PCPs, and repeated assessments made within patients for some outcomes, such as health risk behaviors. Because different patient samples will be surveyed at each time point, within patient correlation over time should not be strong. Still, clustering at the clinic and PCP-levels needs to be examined in all analyses. Third, secular time trends need to be carefully examined and separated from the intervention effect. Based on these considerations, we will focus on model-based approaches (linear or generalized linear mixed effects models) for the main analyses, in addition to standard hypothesis testing techniques.

Aim 1 will compare intermediary targets at all clinics before and after the intervention using an analytic approach that both accounts for design features, repeated assessments within adolescents, time trends in these target behaviors during study period and adjust for potential confounders. For this aim we will use patients as the units of analysis. We will consider outcomes at the level of the patient (adolescent reported motivation for health and provision of appropriate preventive counseling).

Our primary analysis will be based on a set of mixed effects regression models. As an illustration, let's consider the adolescent self-reported health motivation (readiness to change, as other adolescent reported outcomes can be modelled in a similar fashion. Specifically, we will consider the following regression model:

$$Y_{ijk} = \mu + \alpha X_{ijk} + \beta_k T_k + \gamma_k X_{ijk} * T_k + b_i + b_{ij} + \varphi \text{Covariates} + \varepsilon_{ijk},$$

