in which Y_{ijk} denotes the health motivation reported by j th patient within i th provider at k th time interval, X_{ijk} is a binary indicator of exposure to the intervention for the provider and the predictor of interest, T_k is a binary indicator of the k th assessment, b_i and b_{ij} are PCP and adolescent specific random effects that account for the within PCP and within adolescent correlations, and ε_{ijk} is the error term. Additional patient-level or PCP-level confounding variables can be adjusted in the model as well.

With this model, the fixed effects α captures the treatment effects on mean responses and time-by-intervention interaction coefficients γ_k 's captures the treatment effects across time. Fixed effects β_k 's aim to capture any temporal trend or learning effects. Using this approach, both within-adolescents and between adolescents information will be used to estimate the treatment effects. All coefficients will be tested using Wald test. Also note this

model framework is flexible enough that a patient can be enrolled at any time during the study and the model can accommodate different numbers of post-intervention assessments. For example, for an adolescent enrolled after his/her PCP has received intervention, all X_{ijk} 's would take value 1 for that subject.

We will apply linear mixed effects models for Gaussian outcome Y_{ijk} , and generalized linear mixed effects models for other types of outcomes (e.g., logistic model for binary outcome).

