For *Aim 2*, analyses will be based on patient survey responses to the 8-item satisfaction scale, patient perception of PCP communication, and the summary health risk variable, which will all be treated as continuous response variables. The summary health risk variable constructed from a count of dichotomized key risk behaviors (as shown in Table 2). First, satisfaction levels and risk behaviors will be summarized for each period (pre- and post-intervention) and will be compared using two sample t-tests. For the main analysis, we will apply mixed effects models similar to those proposed in Aim 1 to examine the intervention effect. For patient satisfaction, PCP satisfaction, adolescent's perception of PCP communication and health risk behaviors, the analysis will be cross-sectional comparisons at one day following the primary care visit. Let Y_{ij} denotes the satisfaction at one-day post visit of adolescent j within PCP i , let X_{ij} denote whether the PCP has received intervention at the time of visit, then the following mixed effects model can be applied

$$Y_{ij} = \mu + \alpha X_{ij} + b_i + \varphi \text{Covariates} + \varepsilon_{ij},$$

where b_i accounts for within-PCP correlations for adolescents seen by the same PCP. The fixed effect α captures the intervention effect on the patient satisfaction. Similar model can be applied to PCP outcomes and we can account for within-clinic correlations as well.

When examining the intervention effects on adolescents individual risky behaviors (alcohol use, marijuana use, unprotected sexual activity, depression, physical activity, healthy food consumption, seatbelt and helmet use) at baseline, 3, 6, and 12 months after the primary care visit, same modeling framework as outlined for Aim 1 can be applied.

3.3.3 Heterogeneity of Treatment Effects.

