The goal of any heterogeneity of treatment effects analyses will be to ascertain whether treatment effects vary significantly across subgroups of patients and to identify subgroups of patients that achieve the greatest benefit from part or entire treatment regimen. (PCORI Methodology Standard HT-1) Based on our current knowledge, we hypothesize that treatment effects may vary substantially across age groups (13-15 yrs vs. 16-19 yrs), gender groups (male vs. female), racial groups (White, African American, Asian/American Indian/Pacific Islander, and multi-racial), ethnic groups (Hispanic vs. non-Hispanic), adolescents with differential baseline motivation status (highly motivated adolescents vs. less motivated), and adolescents with differential self-efficacy (high vs. low) (PCORI Methodology Standard HT-2). We recognize the possibility that additional subgroups may

arise in the course of the analyses described above as we identify which factors modify the associations. (PCORI Methodology Standard HT-4) Our stepped wedge design allows us to employ both within participants and between participants information to estimate and compare treatment effects.

As we have outlined in the Statistical Analysis section, the primary analysis will be based on mixed-effects regression models in the following form, for example, when examining PCP outcomes (similar models will be applied to adolescent outcomes):

$$Y_{ijk} = \mu + \alpha X_{ijk} + \beta_k T_k + b_i + b_{ij} + \gamma \text{covariates} + \epsilon_{ijk},$$

in which Y_{ijk} denotes the appropriate preventive counseling rate for j th PCP within i th clinic at time interval k , X_{ijk} is a binary indicator of exposure to the intervention (predictor of interest), T_k is a binary indicator of the k th assessment time interval, b_i and b_{ij} are clinic and PCP specific random effects that account for the within clinic and within PCP correlations, ϵ_{ijk} is the error term. Adjustment for additional clinic-level or PCP-level confounding variables can be incorporated into the model as well. With this model, the fixed effect α captures the treatment effect, while fixed effects β_k 's aim to capture any temporal trend. Using this approach, both within-PCP and between PCP information will be used to estimate the treatment effect.

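### The primary longitudinal model has one time index for two clocks; on its best-supported reading it counts the adolescent's own surveys, so contrasts that include α absorb any drift over the rollout

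*Combined protocol and SAP*

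**What the plan says.** Section 3.3.2 sets the requirement for this design: "secular time trends need to be carefully examined and separated from the intervention effect". The Aim 1 model has the fixed terms α (exposure X), β_k (time T_k) and γ_k (their interaction), with random effects for PCP and adolescent. The β_k are said to "aim to capture any temporal trend or learning effects", and α is described as the treatment effect on mean response.

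The index k is worded in three ways:

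- The outcome in the Aim 1 model is "reported by j th patient within i th provider at k th time interval".
- The same sentence of section 3.3.2 continues: "T_k is a binary indicator of the k th assessment, b_i and b_{ij} are PCP and adolescent specific random effects".
- In the PCP-level version of the model in section 3.3.3, "T_k is a binary indicator of the k th assessment time interval".

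Section 3.3.2 adds that "a patient can be enrolled at any time during the study and the model can accommodate different numbers of post-intervention assessments". For individual risk behaviours at baseline, 3, 6 and 12 months after the visit, it says the "same modeling framework as outlined for Aim 1 can be applied". Table 1 counts T1 to T5 from the visit. No calendar or rollout-period term is printed beside T_k. The optional extra covariates are described as patient- or PCP-level confounders, and calendar time is not named among them.

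**The concern.** If T_k marks the survey wave, an adolescent seen in the first rollout interval and one seen in the last have the same T_k values. The only printed term that follows the calendar across adolescents is X, because section 3.1 introduces the intervention clinic by clinic over time. Season, school year or a change in usual screening would then enter α and α + γ_k as if it were treatment effect, although the plan describes the trend as captured.

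The outcomes at stake are motivation, counselling, follow-up care and the individual risk behaviours. Follow-up care has no T1 measurement. Counselling is measured only at T2, so T_k is constant and its model has no working time term at all.

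**Working it through.** **1. Which clock is k?** Four features favour survey number: the literal definition of T_k, the adolescent random effect, rolling enrolment ("a patient can be enrolled at any time during the study"), and the reuse at months counted from the visit. Three favour rollout interval: the wording for Y, the wording in section 3.3.3, and the remark in section 3.3.2 that different patients are surveyed at each time point. Survey number is better supported but not settled. Neither reading is sufficient. With k as survey number, visit date is unadjusted. With k as rollout interval, the effects at 3, 6 and 12 months promised in section 1.1 have no term.

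**2. Inputs.** From the documents: 6 clinics, about 30 PCPs, about 300 adolescents, and surveys at baseline, 1 day, 3, 6 and 12 months. The plan states no power, SD, ICC or step length to reproduce, and the rollout figure is not available. Assumed: one clinic crossing per step, 7 equal intervals of 2–4 months, even enrolment, total SD 1, PCP variance share 0.01–0.10, within-adolescent correlation 0.4–0.6, linear drift, true effect zero.

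**3. Gap in visit date, X fixed at the index visit.** For a clinic crossing after interval c, control visits average (1 + c)/2 and intervention visits (c + 8)/2. The gap is 7/2 = 3.5 intervals for every c. Pooled over clinics it is 112/21 − 56/21 = 2.67 intervals. The mixed model weights between these two.

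**4. Bias in α, X fixed.** A drift of 0.2 SD is 0.2/7 = 0.029 SD per interval if spread over seven intervals, or 0.2/6 = 0.033 if counted from first to last. The outer bounds are 2.67 × 0.029 = 0.08 and 3.5 × 0.033 = 0.12. Generalised least squares with known variances gives about 0.085–0.11 SD.

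**5. Rejection.** P = 1 − Φ(1.96 − b/SE) + Φ(−1.96 − b/SE).

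- b = 0.085, SE = 0.117: b/SE = 0.73, P ≈ 0.11.
- b = 0.105, SE = 0.118: b/SE = 0.89, P ≈ 0.14.

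**6. X switching with the PCP.** For a drift of 0.1 SD per 12 months, the bias is 0.013–0.014 SD with 2-month steps, 0.023–0.026 with 3-month steps and 0.036–0.039 with 4-month steps. Rescaled to 0.2 SD over seven intervals (14, 21 and 28 months), 0.013 × 0.2/0.117 = 0.022 and 0.039 × 0.2/0.233 = 0.033. Varying the within-adolescent correlation and the drift scaling widens this to about 0.02–0.06 SD.

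| 0.2 SD drift, no true effect | Bias in α (SD) | 5% test of α rejects | Post-visit average rejects |
|---|---|---|---|
| X fixed at visit | 0.085–0.11 | 11–15% | 13–22% |
| X switches with PCP | 0.02–0.06 | 6–9% | 6.5–9.5% (3–4-month steps) |

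With 2-month steps and X switching, the last clinic crosses at 6 × 2 = 12 months. Every 12-month survey is then exposed, and the 12-month contrast cannot be identified.

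**7. What escapes.** With X fixed, linear drift adds slope × (months since T1) to the change from T1 in both groups alike, so every γ_k has zero bias. Follow-up care (T3–T5 only) has no such reference. At 0.2 SD drift with X fixed, its bias is 0.084–0.085 SD, its SE 0.091–0.101 and its rejection rate 13–16%.

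**8. With calendar terms.** Fixed effects for the visit interval bring the bias in α to zero under both codings.

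**The case against.** The strongest reply is that k may be the rollout interval. Section 3.3.3 restates the primary model with interval wording and says that similar models apply to adolescent outcomes. On that reading β_k does adjust for the trend. This stands as a reason not to call the survey-number reading settled. It does not rescue the model, because the effects by time since visit then disappear.

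Second, section 3.3.2 asks for an exposure indicator that varies by PCP and time point, and X carries the subscript k. That points to exposure switching during follow-up, where the α bias is roughly half the fixed-exposure figure or less. This stands, so both codings are shown.

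Third, with X fixed and T1 as reference, α is a difference measured before the visit. Its rejection rate is then a test of baseline difference rather than of treatment, and the γ_k escape linear drift. This also stands. It does not help the post-visit average, follow-up care or counselling, and the plan itself presents α as a treatment effect.

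Fourth, the equation is offered as an illustration, has a covariate slot, and is to be followed by a formal analysis plan. That leaves room for a repair, but nothing printed makes it.

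A reader might go further and infer that β_k carries no calendar information, or that every effect estimate will be biased. The documents do not support either. β_k takes up drift within each adolescent's follow-up (0.025, 0.050 and 0.100 SD at 3, 6 and 12 months for a drift of 0.1 SD per year with X fixed). Bias also needs a real trend, and none is documented.

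**Conclusion.** The concern holds in a limited form. The index k is inconsistently defined and cannot serve both time since visit and calendar time. On the better-supported reading, contrasts that include α are open to rollout drift, contrary to the plan's own requirement and to the role it gives β_k. How large this is depends on the exposure coding, which the plan leaves open, and on the assumed steps, variance shares and drift. At 0.2 SD drift the false α ranges from about 0.02 to 0.11 SD over the two codings. Protection of γ_k is confined to linear drift with X fixed and a T1 reference. The point should be settled before analysis, because otherwise estimates could be reported as trend-adjusted when they are not.

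**What to change.** - Define k once, as the survey wave, and keep T_k and γ_k.
- Add a separate set of fixed effects for the calendar rollout interval of the index appointment, or of the survey date if X switches during follow-up. Put them in the Aim 1 model, wherever Aim 2 reuses it for individual risk behaviours, and in the counselling model.
- State whether X is fixed at the visit or switches with the PCP.
- State which contrast (α, γ_k or a post-visit average) is the effect estimate for each outcome.
- Reword β_k as time since the visit and assign the secular trend to the new terms. Align the wording of k in section 3.3.3.

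The change is SAP text and one more set of terms. Appointment dates are already collected (section 4.4); survey dates must be kept in the analysis file if they are used.

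The price is precision. With X fixed, the SE of α rises by roughly 25–35% in the interaction model (0.117 to 0.148–0.157, a figure that also includes a clinic effect). Without the interaction it rises more (0.091 to 0.125, or 37%; 0.096 to 0.141, or 47%). With X switching and a linear calendar term, the rise is about 3–10% (for example 0.058 to 0.060, or 0.064 to 0.070). A full set of survey-date intervals would cost more than that.

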2.1. Sample Size

We plan to enroll approximately 300 adolescent (age 13-18) and parent dyads who have an appointment with a participating provider affiliated with one of six participating practices in the Puget Sound Pediatric Research Network (PSPRN). We also plan to enroll approximately 30 PSPRN providers (about 5 providers per clinic).

2. Gender of Subjects

This study does not have any gender-based restrictions. However, given that women are more frequently primary caregivers and PCPs, we estimate the following gender distribution in our study population:

Adolescents: 150 Females and 150 Males

Caregivers: 240 Females and 60 Males

PCPs: 18 Females and 12 Males

3. Age of Subjects

Participants will include adult *caregivers and PCPs* (over the age of 18 years) and *adolescents* (age 13-18). As health risk behaviors typically begin in adolescence and persist into adulthood, we are targeting adolescents rather than children less than 13 years of age.

4. Racial and Ethnic Distribution

The proposed study population will include a wide cross section of adolescent patients and their caregivers, including many families of ethnoracial minority status. We will monitor diversity in our sample throughout the course of recruitment and adapt recruitment efforts as needed to assure a representative sample. The Central Puget Sound geographic area, where our study population is situated, consists of the following approximate ethnic and racial breakdown:

- 73% White
- 5% African American
- 12% Asian, Hawaiian or Other Pacific Islander
- 1% American Indian or Alaska Native
- 9% some other race (alone) or two or more races

In addition, 9% of individuals in this geographic area are of Hispanic or Latino ethnic background.

5. Inclusion Criteria

Eligible caregivers will have a child 13 to 18 years old who has an appointment with a participating provider at a PSPRN clinic and will be able to understand English.

Eligible adolescents will be 13 to 18 years old, have an appointment with a participating provider at a PSPRN clinic and will be able to understand English.

Eligible PCPs will include providers (i.e., pediatricians, family practitioners, physician assistants and nurse practitioners) affiliated with a PSPRN clinic who are following a panel of adolescent patients and will be able to understand English.

6. Exclusion Criteria

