3.1. Study Design

This study will evaluate the effect of I-ACT with Check Yourself on adolescent-perceived quality of care (i.e., satisfaction and perception of PCP communication), motivation for health, and health risk behaviors using a stepped wedge study design. The study will take place in 6 participating PSPRN affiliated clinics, where the system of interventions (I-ACT with Check Yourself) will be rolled-out sequentially to the clinics, chosen in random order, over spaced time intervals (see Figure 1). We refer to pre-implementation of I-ACT with Check Yourself, as the control period and post-implementation as the intervention (i.e., case) period.

Figure 1: Stepped Wedge Study Design and Timeline

We anticipate that approximately 30% of youth approached will participate in the study. Thus, we will invite approximately 1000 adolescent/caregiver dyads to participate in the study, in order to yield 300 adolescent/caregiver dyad participants in our total sample. Upon enrollment, caregiver participants will be asked to complete a brief (10-minute) web-based questionnaire about their education/occupation, their adolescent's health history, and an open-ended question about what they would like to get from PCPs for themselves and their adolescent. Adolescents who enroll in the study will receive either electronic health screening alone (i.e., control group) if

their clinic appointment occurs in the pre-I-ACT implementation period or Check Yourself (i.e., intervention group) if their clinic appointment occurs in the post-implementation period.

At baseline (T1), adolescents will be asked to complete a web-based screening survey that includes questions about guideline-recommended health risk behavior screening areas, including substance use, nutrition, physical activity, sexual behavior, depressive symptoms, and safety. The screener questions themselves are current standard of care. Adolescents will also be asked to report their age, gender, race/ethnicity, interest in discussing health risks with the PCP, and self-efficacy.

Adolescents in the control group will complete the web-based screening survey for research purposes, but neither they nor their PCP will receive feedback about their health behaviors. PCPs will screen and counsel the patient as they would normally do under usual care conditions, consistent with the current standard of care.

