3.2. Measures by Construct and Time point

Tables 1 and 2 describe the study measures by construct.

Table 1: Measures used in the study, organized by construct and method.

Measures and Constructs	Time point
Moderators	
Gender, age, race, household composition, school, truancy, support, goals, interest in discussing health risks with provider	T1(A)
Number of visits with provider	T2(A)
Health Self-Efficacy	T1(A), T2 (A), T3(A), T4(A), T5(A)
Caregiver Concerns	
Guidelines for Adolescent Preventative Services Caregiver Questionnaire: adolescent health risk behavior concerns.	T1(C)
Perception of provider engagement with the caregiver	T2 (C)
Intermediary Targets	
Health Motivation (Readiness to Change Rulers): Self-report used to assess adolescent motivation for change among specific health behaviors.	T1(A), T2 (A), T3(A), T4(A), T5(A)
Adolescent Report of the Visit: adolescent-report of the PCPs' delivery of risk behavior screening and counseling based on risk level.	T2 (A)
Interval Receipt of Care: adolescent self-report of extent of follow up care.	T3 (A), T4(A), T5(A)
Main Outcomes: Satisfaction & Perception of PCP Communication	

Satisfaction Questionnaire: self-report of satisfaction with care based on items adapted from the Consumer Assessment of Healthcare Providers and Systems (CAHPS) measure.	T2(A/C)
Adolescent Perception of Patient-Centeredness: adolescent self-report of how adolescents feel about visits with their primary caregiver.	T2(A)
Main Outcomes: Health Risk Dimensions*	
Alcohol Consumption and Marijuana Use: self-report based on items about typical quantity and frequency of drinking, smoking/using tobacco, and marijuana use (each calculated separately) over the past 30 days.	T1(A), T3(A), T4(A), T5(A)
Fruit and Vegetable Screener: self-report of fruit and vegetable consumption.	T1(A), T3(A), T4(A), T5(A)
Physical Activity Screener: self-report of physical activity.	T1(A), T3 (A), T4(A),T5(A)
Sexual Risk: self-report of sexual activity, birth control, and condom use.	T1(A), T3(A), T4(A), T5(A)
Patient Health Questionnaire-9 (PHQ-9): self-report of DSM-V symptoms for depression.	T1(A), T3(A), T4(A), T5(A)
Safety: self-report to assess behaviors that contribute to unintentional injuries (e.g., seat belt use, helmet use).	T1(A), T3(A), T4(A), T5(A)

Key: T1 = Timepoint 1 (Baseline) T4 = Timepoint 4 (6 month)
T2 = Timepoint 2 (1-day) T5 = Timepoint 5 (1 year)
T3 = Timepoint 3 (3-month)
A = Adolescent survey

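### The printed adolescent-outcome models omit the clinic, which is the randomised unit, while section 3.3.3 gives a primary form that includes it; the passages need to be reconciled

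*Combined protocol and SAP*

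**What the plan says.** Section 3.1 states that the intervention "will be rolled-out sequentially to the clinics, chosen in random order", and there are six clinics. Section 2.1 adds: "We also plan to enroll approximately 30 PSPRN providers (about 5 providers per clinic").

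The random effects are then described in several ways.

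- **Section 3.3.2, general remarks.** PCPs are recognised as nested in clinics, and "clustering at the clinic and PCP-levels needs to be examined in all analyses". The same paragraph says that "secular time trends need to be carefully examined and separated from the intervention effect".
- **Section 3.3.2, Aim 1 equation.** "b_i and b_{ij} are PCP and adolescent specific random effects that account for the within PCP and within adolescent correlations". There is no clinic term. The time indicator refers to the assessment, and coefficients get Wald tests. The equation is offered as an illustration, but "other adolescent reported outcomes can be modelled in a similar fashion".
- **Section 3.3.2, Aim 2 equation.** It has a PCP random effect only, and no time term. The possibility of handling within-clinic correlation is mentioned in a sentence about PCP outcomes.
- **Section 3.3.3.** The primary form, presented as the one already set out, has clinic and PCP random effects. It is illustrated with PCP outcomes, and adolescent outcomes are to receive similar models.

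Table 1 lists the satisfaction questionnaire, the adolescent report of the visit and the patient-centeredness measure ("Adolescent Perception of Patient-Centeredness: adolescent self-report of how adolescents feel about visits with their primary caregiver") at T2 only.

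**The concern.** In a stepped wedge, adolescents from one clinic share whatever makes that clinic different, and exposure is assigned to the clinic as a whole. A PCP intercept takes up part of that shared variation, but it treats the five PCPs of a clinic as independent. The part of the comparison that runs between clinics is then credited with more information than it holds.

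Section 3.3.3 can be read as a commitment to a clinic effect in the adolescent models. It can equally be read as the same two-level template moved up one level, with clinic and PCP replacing PCP and adolescent. The text does not settle which, so two analysts could each follow the plan and report different standard errors for the same outcome.

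**Working it through.** **Inputs from the plan.** 6 clinics, about 30 PCPs and about 300 adolescents (section 2.1), so 300/30 = 10 per PCP and 300/6 = 50 per clinic. The plan gives no ICC, standard error or worked sample size, so there is no figure of its own to reproduce. Figure 1 is not shown, and recruitment is rolling by clinic (section 6.1), so the actual splits are unknown.

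**Assumptions.** Total variance 1; PCP share 0.03; clinic ICC ρ = 0.01, 0.02 or 0.05, constant over time; equal cluster sizes; PCPs share their clinic's split; two-sided 5%. For one clinic per step: even enrolment over 7 periods, giving pre/post counts per clinic of 8/42, 15/35, 21/29, 28/22, 36/14 and 43/7.

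**Formulas for the printed Aim 2 model.** Let p be the post fraction in a clinic and p̄ its mean (149/300 = 0.497).

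- Within part: W = Σ 50p(1−p) = 57.82. Between part: B = Σ 50(p−p̄)² = 17.18.
- Residual variance: σ² = 0.97 − ρ.
- The PCP term absorbs the clinic variance, so the model uses λ = σ² + 10(0.03 + ρ). The true between-clinic value is λ* = σ² + 10(0.03) + 50ρ.
- Model variance of alpha = 1/I, with I = W/σ² + B/λ. True variance = J/I², with J = W/σ² + Bλ*/λ².
- Model SE / true SE = √(I/J). Type I error = 2[1 − Φ(1.96√(I/J))].

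| ρ | σ² | λ | λ* | I | J | SE ratio | Type I error |
|---|---|---|---|---|---|---|---|
| 0.01 | 0.96 | 1.36 | 1.76 | 72.86 | 76.57 | 0.975 | 5.6% |
| 0.02 | 0.95 | 1.45 | 2.25 | 72.71 | 79.24 | 0.958 | 6.0% |
| 0.05 | 0.92 | 1.72 | 3.72 | 72.83 | 84.45 | 0.929 | 6.9% |

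**Other layouts.** Two clinics per step (post fractions 0.75, 0.50, 0.25): W = 62.50, B = 12.50, giving 5.4%, 5.7%, 6.3%. Three per step (2/3, 1/3): W = 66.67, B = 8.33, giving 5.3%, 5.5%, 5.8%. When the variance components are estimated by REML, the PCP term absorbs slightly less than the full clinic variance, and the upper ends become about 7.3%, 6.5% and 5.9%.

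**When nothing goes wrong.** If every clinic has the same split, B = 0 and J = I. If ρ = 0, λ* = λ and J = I. Both give 5.0%.

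**REML simulation** (10,000 runs per scenario, Monte Carlo SE 0.2-0.3 points, one clinic per step), rejection rates:

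| Model | ρ = 0 | 0.01 | 0.02 | 0.05 |
|---|---|---|---|---|
| Printed Aim 2, PCP only | 5.2% | 5.7% | 6.6% | 7.3% |
| Printed Aim 2 + clinic intercept | 5.2% | 5.4% | 5.8% | 5.8% |
| Period terms added, PCP only | 5.2% | 7.0% | 8.0% | 10.2% |
| Period terms added + clinic intercept | 5.2% | 6.0% | 6.1% | 6.5% |

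The last two rows concern a model with calendar-period terms, which neither printed adolescent equation has. For its PCP-only form, the known-variance figures are 6.2%, 7.1% and 8.9%. With period terms, the same 25/25 split in every clinic no longer protects: 5.4%, 5.8%, 7.0%.

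**Aim 1.** With five assessments and an assumed adolescent share of 0.40, the known-variance error for alpha is 5.4%, 5.7% and 6.1%, and 5.0% for the gamma_k. If T1 is the reference level, alpha is the difference at T1, before the visit, and the post-visit effect lies in gamma_k. A constant clinic effect cancels from those within-adolescent contrasts.

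**The case against.** The strongest reply is that clinic clustering is not overlooked. Section 3.3.2 names the nesting and asks for it to be examined everywhere, the Aim 1 equation is only an illustration, section 3.3.3 puts clinic in the primary form, and "an analysis plan will be formally presented to the study team and Project Advisory Board" before each research question is analysed. This stands to the extent that a reader who infers that the plan ignores clinics would be wrong. It does not close the gap: examining clustering is not a model term, no rule says when a term would be added, and the illustrative equation is the template for the other adolescent outcomes.

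The second reply is that the effect is small and rests on assumed ICCs. That also stands. At a clinic ICC of 0.01 the simulated gain from the clinic intercept (5.7% to 5.4%) is within one to two Monte Carlo standard errors.

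Third, a reader might take the 6-10% range as the error of the printed model. The documents do not support that. The range arises only if period terms are added to PCP-only random effects, a combination that no passage prints. It is relevant because section 3.3.2 wants secular trends separated from the intervention effect.

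Fourth, a reader might infer that all Aim 1 effects are compromised. For outcomes measured at T1 the gamma_k tests are not disturbed by a constant clinic effect.

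**Conclusion.** The concern holds as an inconsistent and uncommitted specification that should be fixed. If the printed equations are followed, clinics differ and splits vary across clinics, the standard error of alpha is too small. The printed Aim 2 error rate is then about 5.6-7.3% with one clinic per step, 5.4-6.5% with two and 5.3-5.9% with three. If period terms are added without a clinic term, it is about 6-10% with one clinic per step.

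The exposure is mainly outcomes without a baseline measure, chiefly the T2-only ones (satisfaction, patient-centeredness, report of the visit), where alpha is the whole effect.

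These sizes rest on a PCP share of 0.03, clinic ICCs of 0.01-0.05, equal cluster sizes and a constant clinic effect, none of which the plan states. Moving the PCP share from 0.01 to 0.05 changes the known-variance Aim 2 figure at clinic ICC 0.05 from 7.3% to 6.5%. Binary outcomes and unequal cluster sizes were not simulated. Confidence is medium.

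**What to change.** Reconcile sections 3.3.2 and 3.3.3 by stating that every adolescent-outcome model includes a clinic random intercept alongside PCP, and adolescent where assessments repeat. State the assumed ICCs. The analysis plan already promised in section 3.3.2 is a natural place.

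The cost is SAP wording and some precision. Median 95% half-widths in the simulation at clinic ICC 0 and 0.05:

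- Printed Aim 2 model: 0.228 to 0.231 (+1%) and 0.228 to 0.235 (+3%).
- With period terms: 0.317 to 0.324 (+2%) and 0.322 to 0.349 (+8%).

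A small-sample method for six clinics is optional and the team's choice. The Wald test with clinic and PCP effects was already at 5.2-5.8% in the printed model, and up to 6.5% with period terms.

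- **Clinic as fixed effects** stayed near 5%, but widens intervals by 8-11%, or 20-25% with period terms.
- **A permutation test over rollout orders** is usable with 6! = 720 orders (one clinic per step) or 6!/(2!2!2!) = 90 (two per step). With three per step there are 6!/(3!3!) = 20 orders, so the smallest two-sided p is 1/20 = 0.05 without period terms. With them, exchanging the two groups only reverses the sign of alpha, so orders tie in pairs and the smallest p is 2/20 = 0.10. It should not be relied on in that layout.
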